RESPONSE: Functional endoscopic sinus surgery (FESS) is a commonly performed procedure in the United States to treat chronic rhinosinusitis. Common practice is to prescribe prophylactic antibiotics postoperatively. This is similar to the long tradition of prophylactic antibiotics after tonsillectomy. The American Academy of Otolaryngology - Head and Neck Surgery recently strongly recommended against prophylactic antibiotics after tonsillectomy. In this light, this study would demonstrate the lack of need for antibiotics after FESS. Currently [name] does not prescribe antibiotics except when evidence of active infection was found during surgery. [name] currently prescribes antibiotics. This study would prospectively compare the two groups in a randomized fashion. Two previous studies have been performed (Jiang et al. Postoperative antibiotic care after functional endoscopic sinus surgery. *Am J Rhinol* 22, 608-612, 2008); (Albu, et al. Prophylactic antibiotics in endoscopic sinus surgery: A short follow-up study. *Am J Rhinol* 24 306-309, 2010.) These studies were both randomized, placebo controlled prospective studies. Albu et al found that amoxicillin/clavulanate improved the outcome in the "early blood crust healing" and the endoscopic score was improved. Jiang et al. showed that amoxicillin/clavulanate did not improve short term outcomes of FESS. Both studies were limited by a lack

of a prospective instrument to evaluate symptoms. We plan to use the Sinonasal outcomes test -22 (SNOT-22), which is a validated quality of life instrument in sinusitis.

4) What is the estimated completion date? (MM/YYYY)

RESPONSE: 06/2015

5) Who specifically (name, title, and department) is going to perform the coordinator function? Discuss his/her relevant qualifications (training, education, experience):

The PI, [name], has assumed coordinator function. He has had experience and training through the Harvard Catalyst education offerings in clinical studies.

6a) Who is going to supervise the study coordinator(s)? When applicable, indicate if support and oversight will be provided by the Ophthalmology Clinical Research Office (OCRO).

6b) Describe the PI's plan to provide adequate training, and supervision (e.g., regular meetings, training opportunities):

[name] will be supervising all aspects of the study and meets regularly (weekly) with [name] on matters of enrollment, patient compliance, and monitoring of adverse events.

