- 25) Will there be any out-of-pocket costs to subjects and/or expenses likely to be covered by their insurance for participating in the study? YES NO

IF YES, please specify in detail the costs to subjects and/or their insurance (e.g. co-pays):

RESPONSE: The study drug is provided by the pharmacy free of charge. The study medication supplies are charged to the study's cost center by the pharmacy.

- 26) If applicable, how will the cost of reasonably foreseeable medical care in the event of a research-related injury be covered (e.g., sponsor agreement, likely to be covered by insurance, grant, departmental funds)?

RESPONSE: This would be covered by patients' insurance.

RISK

Risk is the probability and magnitude of harm or discomfort anticipated as a result of participation in the research. Any risks of harm to subjects and/or anticipated discomfort(s) that are reasonably foreseeable, even if unlikely, and the safeguards in place to minimize these risks and discomfort(s) must be identified and discussed below. Risks of harm and discomfort may include: physical harm/discomfort, psychological harm/discomfort, legal harm/discomfort, social harm/discomfort, and economic harm.

- 27) Describe any risks of harm to subjects that are reasonably foreseeable, even if unlikely:

These are listed below:

1. amoxicillin/clavulanate arm:
From the FDA monograph
Gastrointestinal

Diarrhea, nausea, vomiting, indigestion, gastritis, stomatitis, glossitis, black “hairy” tongue, mucocutaneous candidiasis, enterocolitis, and hemorrhagic/pseudomembranous colitis. Onset of pseudomembranous colitis symptoms may occur during or after antibiotic treatment

Hypersensitivity Reactions

Skin rashes, pruritus, urticaria, angioedema, serum sickness–like reactions (urticaria or skin rash accompanied by arthritis, arthralgia, myalgia, and frequently fever), erythema multiforme (rarely Stevens-Johnson syndrome), acute generalized exanthematous pustulosis, and an occasional case of exfoliative dermatitis (including toxic epidermal necrolysis) have been reported. These reactions may be controlled with antihistamines and, if necessary, systemic corticosteroids. Whenever such reactions occur, the drug should be discontinued, unless the opinion of the physician dictates otherwise. Serious and occasional fatal hypersensitivity (anaphylactic) reactions can occur with oral penicillin.

Liver

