A moderate rise in AST (SGOT) and/or ALT (SGPT) has been noted in patients treated with ampicillin-class antibiotics but the significance of these findings is unknown. Hepatic dysfunction, including increases in serum transaminases (AST and/or ALT), serum bilirubin, and/or alkaline phosphatase, has been infrequently reported with Augmentin. It has been reported more commonly in the elderly, in males, or in patients on prolonged treatment. The histologic findings on liver biopsy have consisted of predominantly cholestatic, hepatocellular, or mixed cholestatic-hepatocellular changes. The onset of signs/symptoms of hepatic dysfunction may occur during or several weeks after therapy has been discontinued. The hepatic dysfunction, which may be severe, is usually reversible. On rare occasions, deaths have been reported (less than 1 death reported per estimated 4 million prescriptions worldwide). These have generally been cases associated with serious underlying diseases or concomitant medications.

Renal

Interstitial nephritis and hematuria have been reported rarely. Crystalluria has also been reported

Hemic and Lymphatic Systems

Anemia, including hemolytic anemia, thrombocytopenia, thrombocytopenic purpura, eosinophilia, leukopenia, and agranulocytosis have been reported during therapy with penicillins. These reactions are usually reversible on discontinuation of therapy and are believed to be hypersensitivity phenomena. A slight thrombocytosis was noted in less than 1% of the patients treated with Augmentin. There have been reports of increased prothrombin time in patients receiving Augmentin and anticoagulant therapy concomitantly.

Central Nervous System

Agitation, anxiety, behavioral changes, confusion, convulsions, dizziness, insomnia, and reversible hyperactivity have been reported rarely.

Miscellaneous

Tooth discoloration (brown, yellow, or gray staining) has been rarely reported. Most reports occurred in pediatric patients. Discoloration was reduced or eliminated with brushing or dental cleaning in most cases.

2. Placebo Arm:

The main theoretical risk from not giving antibiotics post operatively would be a risk of postoperative infection. This would manifest as sinusitis-like symptoms. Worst case scenario would result in complications of sinusitis (orbital infection, meningitis, brain abscess). These complications are rare, and [name] has not experienced them while not giving routine postoperative antibiotics as is his usual practice.

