3. Privacy:

Personal data will be collected from subjects. The data will be saved under a unique subject number, which will remove personal identifying information from the research data. Data will be secured under a password protected computer in a locked office of the PI.

28) If applicable, describe any group harms (i.e., research that focuses on a specific group or population):

RESPONSE: NA

29) Do you anticipate any circumstances in which a “breach of confidence” associated with a mandated disclosure (e.g. reporting abuse to authorities) may occur as part of this study?

RESPONSE: No we do not anticipate a breach of confidence

30) In the view of the PI, what risk classification (taking into consideration the probability and magnitude of harm) is appropriate for the proposed research?

Minimal Risk Greater than Minimal Risk Unknown

Minimal risk means the probability and magnitude of harm or discomfort anticipated in the research are not greater in and of themselves than those ordinarily encountered in daily life or during the performance of routine physical or psychological examinations or tests.

31) Please explain why you feel this category is appropriate based on the definition above (when more than minimal risk describe the likelihood and seriousness of such risks):

RESPONSE: In patients that are randomized to receive post operative antibiotics, there is a risk of adverse reaction to augmentin as detailed above. For patients that are randomized to placebo, there is a risk of post operative infection as detailed above as well. We believe the study is low risk to participants, however as defined above, it is more than the risk encountered in daily life.

32) What provisions are in place to minimize harm or discomfort?

RESPONSE: Patients are seen one week after surgery to undergo endoscopic evaluation to ensure that the patient is healing well without evidence of infection. At all times during the day they can call the sinus center to speak to a nurse if they have any concerns. At night there is a resident on call to answer questions and the MEEI ED is always open.

ALTERNATIVES

33) Describe any alternatives, especially other treatment(s) that are available to potential patients outside of the research:

RESPONSE: If patients do not elect to enroll in the study, they would receive standard post-operative care. They would be prescribed antibiotics at the discretion of the surgeon.

BENEFITS

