- 34) Are there any potential direct benefits to individual subjects related to the research?
 YES NO

IF YES, please explain (address whether these benefits (e.g., clinical, therapeutic) would be available to subjects outside of the research):

RESPONSE:

- 35) Explain the potential benefits to science, and/or society (indirect benefits) which may accrue as a result of this research:

RESPONSE: Antibiotic resistance is growing in the world, and this study may provide prospective, randomized data that antibiotics do not result in a benefit to patients. Hopefully surgeons would stop giving postoperative antibiotics, and decrease the risk of side-effects from antibiotics (allergic reactions, clostridium difficile infection, GI upset, etc) to future patients. Also health care costs would be decreased by reducing antibiotic prescriptions.

- 36) If more than minimal risk, address how risks relate to benefits:

RESPONSE: While not “minimal risk”, the risk to patients is low, as detailed above. Many patients have adverse reactions to antibiotics, and if this study shows that the outcomes of patients undergoing sinus surgery without antibiotics are not worse, then hopefully less patients will be prescribed antibiotics.

CONSENT PROCESS

- 37) Describe the consent process in detail. Include who specifically will be obtaining consent, describe their knowledge/experience in obtaining consent from research subjects, and include the location where study information will be exchanged, how (consent form, orally, information sheet, etc.) information is being conveyed to subjects, and when the consent will be obtained (e.g. during pre-surgical visit, about one week before the screening visit):

RESPONSE: Consent will be obtained by [name], [name] or [name] in the clinic during the subject's preoperative visit in the MEEI sinus center. There is a formal consent form that is signed by patients and an oral script (these are on IRBNET). Subjects can think about the study and opt out of randomization at the time of surgery (usually 2-4 weeks elapse between preoperative visit and surgery).

- 38) Indicate which of the following consent procedures you are contemplating for this research:

Written consent form

- Short form process (only appropriate for minimal risk studies)
** If checked, answer question 42 below.*
- Assent from adults with diminished decision-making capacity
**If checked, provide justification below:*
- Assent from children and parental permission

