### **Statistical Analysis Plan**

The primary endpoint was the overall change in SNOT-22 scores from baseline to the final study visit. Secondary outcomes included the change in LK Endoscopic Score from the same time points, as well as rates of post-operative infection. Additional exploratory analyses included the effect of baseline clinical factors, including baseline sinus culture results, history of prior sinus surgery, comorbid asthma, and presence of nasal polyps.

The primary outcome and secondary outcome were analyzed using a repeated-measures analysis of variance (ANOVA) to assess for a group x time interaction on clinical scores. For the secondary analysis of the primary outcome, this model was modified to include baseline clinical covariates in a repeated-measures analysis of covariance (ANCOVA).

The achieved power for non-inferiority was calculated via the same methods as the prospective power analysis. Rather than an *a priori* estimate of standard deviation in scores, the achieved power was based on the actual number of randomized subjects and the actual pooled standard deviation of post-treatment SNOT-22 scores in the two groups. The non-inferiority margin was 9 units on the SNOT-22.

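### Adverse-event monitoring is mentioned but has no method or time window, and the SAP compares infection between arms but no antibiotic side-effect

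*Protocol*

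**What the plan says.** **Risks named.** Protocol item 31 sets out one risk per arm: a reaction to the antibiotic in one, post-operative infection in the other. The item 27 list gives timing for two of the antibiotic harms. For colitis: "Onset of pseudomembranous colitis symptoms may occur during or after antibiotic treatment". For the liver: "The onset of signs/symptoms of hepatic dysfunction may occur during or several weeks after therapy has been discontinued".

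**Checks described.** Item 32, on minimising harm, gives one scheduled assessment: "Patients are seen one week after surgery to undergo endoscopic evaluation to ensure that the patient is healing well without evidence of infection". The rest of that answer depends on the patient making contact: "At all times during the day they can call the sinus center to speak to a nurse if they have any concerns", and "At night there is a resident on call to answer questions and the MEEI ED is always open". Elsewhere, item 6b describes weekly supervision meetings "on matters of enrollment, patient compliance, and monitoring of adverse events", and the delegation table in item 7 assigns evaluation of adverse reactions to physicians.

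**Reasons given for the trial.** Item 35 hopes that the result would "decrease the risk of side-effects from antibiotics (allergic reactions, clostridium difficile infection, GI upset, etc) to future patients". It also cites antibiotic resistance and health care costs.

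**Outcomes analysed.** In the SAP's first paragraph the primary endpoint is change in SNOT-22. It continues: "Secondary outcomes included the change in LK Endoscopic Score from the same time points, as well as rates of post-operative infection". The exploratory analyses concern baseline clinical factors. No outcome covers gastrointestinal upset, colitis, rash, hypersensitivity or liver events.

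**The concern.** The question is a trade-off: does leaving out the antibiotic cost patients anything, and what do they gain? The plan measures the first half through symptoms, endoscopic score and infection. It names no outcome for the second half.

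This matters most for a mixed result. Suppose placebo shows a small excess of infection, or a SNOT-22 difference inside the 9-unit non-inferiority margin. A reader would want to set that against side-effects avoided in the same randomised patients, and the planned analyses would not supply the figure.

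There is also a participant-safety side. A nasal endoscopy looks at healing and infection; it does not show colitis, rash or liver dysfunction. By the protocol's own account, two of these can begin after treatment ends. Unless someone asks about them at a set time, detection depends on the patient making contact or on an evaluation whose content and timing are not described.

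**Working it through.** The plan gives no figure to reproduce on this point, so the first check is a reading.

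**Step 1. Each named risk against what is checked and analysed**

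| Risk (items 27, 31) | Scheduled check aimed at it | Unscheduled or unspecified provision | SAP outcome |
|---|---|---|---|
| Infection (placebo) | One-week endoscopy (item 32) | Nurse line, on-call resident, emergency department | Infection rate, secondary |
| Antibiotic reactions: gastrointestinal, hypersensitivity, liver | None described | The same contacts; weekly oversight (6b); delegated evaluation (7) | None |

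The first row is complete. In the second row monitoring is mentioned, but without questions, dates, a window or a recording method, and nothing carries through to the analysis.

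**Step 2. Timing**

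Colitis may start after treatment and liver dysfunction several weeks after it, so either could begin after the one-week visit. The SAP also refers to a final study visit. The available text gives neither its date nor the duration of study drug, so the length of any uncovered period cannot be calculated.

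**Step 3. What a by-arm comparison could show**

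Inputs: 140 subjects in total (item 11). The allocation ratio is not stated, so 70 per arm is an assumption. The documents give no side-effect rates, so those below are illustrative.

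- Standard error: SE = √[p₁(1−p₁)/70 + p₂(1−p₂)/70]; 95% half-width = 1.96 × SE.
- Power, two-sided 5%: Φ[(|p₁−p₂| − 1.96 × SE₀)/SE], where SE₀ uses the pooled rate.

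| Antibiotic vs placebo | SE | Difference and 95% CI (points) | Power |
|---|---|---|---|
| 15% vs 5% | √(0.1275/70 + 0.0475/70) = 0.050 | 10 ± 9.8 (0.2 to 19.8) | about 50% |
| 20% vs 5% | √(0.1600/70 + 0.0475/70) = 0.054 | 15 ± 10.7 (4.3 to 25.7) | about 77% |
| 25% vs 5% | √(0.1875/70 + 0.0475/70) = 0.058 | 20 ± 11.4 (8.6 to 31.4) | about 92% |

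With a 10% rate on placebo, the half-width is 12.3 points against 25% and 12.8 against 30%.

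**Step 4. Rare events**

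- Chance of seeing at least one case of a 1% event in 70 patients: 1 − 0.99⁷⁰ = 0.51.
- One-sided 95% upper bound after zero events in 70: 1 − 0.05^(1/70) = 0.042, or 4.2%.

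The sample can therefore describe common side-effects, roughly at the lower rates and clearly at the higher ones. It cannot compare rare late colitis or liver events.

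**The case against.** The other side has five fair points.

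- **Safety oversight exists.** A reader might infer that the one-week endoscopy is the only safety check. The documents do not support that: item 32 adds three routes of contact, item 6b covers adverse events weekly, and item 7 delegates their evaluation. Item 32 is also an answer about minimising harm, not a schedule of assessments. This stands. The gap is one of method, timing and analysis, not of monitoring as such.
- **One harm is analysed.** A reader might infer that the SAP has no harm outcome. Post-operative infection is one, and it is the main risk named for placebo. What is missing is any antibiotic side-effect.
- **Side-effects are not the sole rationale.** Item 35 opens with resistance and also cites cost. Item 36 treats antibiotic reactions as already known and asks whether outcomes without antibiotics are no worse. So the primary claim does not depend on a harms comparison. That stands, but items 35 and 36 still invoke avoided side-effects, and a trial-based estimate would let readers weigh them.
- **The late window may already be covered.** The final visit could fall several weeks after the last dose. The available text can neither confirm nor exclude this, so it would be wrong to say that late events will be missed. Item 27 also calls liver dysfunction infrequent and usually reversible.
- **It may be late to change collection.** The SAP is written in the past tense and refers to the number actually randomised. New questions cannot be put to past visits; only recorded reactions can be tabulated.

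None of these removes the central fact that the SAP's outcome list contains no antibiotic side-effect.

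**Conclusion.** The point holds in this limited form and is worth acting on. Of the two arm-specific risks in item 31, the placebo-arm risk has a dated check and a between-arm comparison. The antibiotic risk has monitoring without a stated method or window, and no comparison. The trial can therefore report the cost of withholding antibiotics but not the cost of giving them.

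The outcome list rests on the text alone. The size of the gain rests on assumptions: with 70 per arm and the illustrative rates against 5%, a comparison would carry about ±10 to 11 points. That is useful for common side-effects and uninformative for rare ones.

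The gap does not invalidate the primary analysis, and it does not show that participants are unmonitored or that late harms will go unseen.

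**What to change.** 1. **Collection.** At each existing study visit through the final visit, have someone blind to arm ask every participant a fixed list drawn from items 27 and 35: diarrhea or colitis, rash or hypersensitivity, gastrointestinal upset, jaundice or liver symptoms. Record the answer and date, including when the answer is no.
2. **Window.** State the study-drug duration and the final visit date, so that readers can see how much of the onset period in item 27 is covered.
3. **Analysis.** Add a secondary safety outcome to the SAP: the proportion with any listed event by arm, with the difference and 95% CI, shown beside the infection difference. Present it as estimation, and say that it is not informative for rare events.
4. **Participants already completed.** Tabulate by arm the adverse reactions recorded under the item 7 delegation. State that collection was unsolicited unless study records show that it was solicited, and keep these data separate from checklist data.

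The cost is a short checklist at visits that already take place and one table. No extra patients, procedures or visits are needed.

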### **Statistical Analysis Plan**

The primary endpoint was the overall change in SNOT-22 scores from baseline to the final study visit. Secondary outcomes included the change in LK Endoscopic Score from the same time points, as well as rates of post-operative infection. Additional exploratory analyses included the effect of baseline clinical factors, including baseline sinus culture results, history of prior sinus surgery, comorbid asthma, and presence of nasal polyps.

The primary outcome and secondary outcome were analyzed using a repeated-measures analysis of variance (ANOVA) to assess for a group x time interaction on clinical scores. For the secondary analysis of the primary outcome, this model was modified to include baseline clinical covariates in a repeated-measures analysis of covariance (ANCOVA).

The achieved power for non-inferiority was calculated via the same methods as the prospective power analysis. Rather than an *a priori* estimate of standard deviation in scores, the achieved power was based on the actual number of randomized subjects and the actual pooled standard deviation of post-treatment SNOT-22 scores in the two groups. The non-inferiority margin was 9 units on the SNOT-22.

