- Adults with Decisional Impairment- If checked, please describe below the type and range of decisional impairment and a rationale for why it is necessary to include adults with decisional impairment:
- Other Populations with Potentially Diminished Capacity (i.e., socially, educationally, economically disadvantaged, elderly, terminally ill) - If checked, specify population below and describe what additional safeguards will be in place to protect the rights and welfare of these subjects:

RESPONSE: We have enrolled approximately 25 patients so far. We would prefer to enroll non-english speaking patients. We are aware of the new IRB protocol regarding non English speaking patients' consent. We would like to apply for the "short-form" consent process in order to continue to enroll non-English speaking patients.

- 14)** Explain how the Investigator has access to a population that would allow recruitment of the required number of subjects within the proposed timeframe:

RESPONSE: [name] and [name] both have busy rhinology practices from which to enroll patients.

- 15)** If subjects are recruited from the investigator's patient population or MEE/SERI employees will be recruited, describe what measures are taken to minimize coercion or undue influence:

RESPONSE: The investigators discuss with the patient the voluntary nature of the study, and the fact that the subjects can withdraw at any time from the study. Also it is discussed with the patient that by not enrolling they will not affect their clinical care at all.

SUBJECT SCREENING/RECRUITMENT

- 16)** Describe any screening methods used to determine eligible subjects (i.e., search of medical records or recruitment databases, completion of screening tests, response to interview questions, etc.):

RESPONSE: Patients will be recruited by [name] and [name] in their clinics from patients that are determined to be candidates for endoscopic sinus surgery and have agreed to undergo surgery. The patient will decide to undergo surgery first, and will then be asked to participate in the study. A script to be used for oral invitation in the study is provided in the application packet.

- 17)** Is [protected health information](#) accessed during the screening process? **YES** **NO**

IF YES, specify the information system(s) and the location of the database(s) you will be accessing during the screening process:

RESPONSE: LMR is accessed for patients' clinical information. This is accessed in the MEEI sinus center.

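### Operating surgeon is absent from the SNOT-22 and LK models; adding surgeon and surgeon x time would be a small, nearly free gain in precision, not the removal of a bias

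*SAP*

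**What the plan says.** In the SAP, "The primary endpoint was the overall change in SNOT-22 scores from baseline to the final study visit". The primary and secondary outcomes are "analyzed using a repeated-measures analysis of variance (ANOVA) to assess for a group x time interaction on clinical scores", and no covariate is named for that model. Covariates appear in two other places. Exploratory analyses look at baseline clinical factors, "including baseline sinus culture results, history of prior sinus surgery, comorbid asthma, and presence of nasal polyps". A secondary analysis of SNOT-22 turns the model into an ANCOVA with baseline clinical covariates. Surgeon is named in neither.

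The protocol's background response (before question 4) describes two physicians. One "does not prescribe antibiotics except when evidence of active infection was found during surgery"; the other "currently prescribes antibiotics". Question 14 says that they "both have busy rhinology practices from which to enroll patients", and question 16 that they recruit "in their clinics from patients that are determined to be candidates for endoscopic sinus surgery and have agreed to undergo surgery". Question 49 puts the pharmacy in charge of randomization. The supplied text does not say whether randomization was stratified by surgeon.

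**The concern.** The protocol itself identifies a two-level practice factor tied to the question under test. Randomization replaces each surgeon's routine postoperative prescribing. It does not equalize technique, case mix or clinical judgement between the two practices. If patients of one surgeon improve more on SNOT-22 or LK than patients of the other, or are recorded as infected more often, that difference sits in the error term of an unadjusted analysis.

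Whether randomization was stratified does not decide the matter. If it was, the arms are balanced on surgeon, and ignoring the stratum makes the reported standard error somewhat larger than it should be. If it was not, the arms can differ by chance in their surgeon mix, and the unadjusted estimate carries that noise. In both cases what is at stake is precision against the 9-unit non-inferiority margin.

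**Working it through.** **Inputs from the documents.** Total enrolment 140 (Protocol, question 11); margin 9 SNOT-22 units (SAP); two recruiting surgeons (Protocol, background and question 14).

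**Not in the supplied text, so assumed.** SD, alpha, target power, allocation ratio, the share of patients per surgeon (q), and any surgeon difference in mean SNOT-22 change (d). I take 1:1 allocation, so 70 per arm, and no dropout.

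**1. A working SD.** The planned 140 cannot be reproduced without an SD, but the SD that fits it can be solved for: SD = 9 / [(z for alpha + z for power) x sqrt(2/70)].

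| One-sided alpha | Power | SD that gives 70 per arm |
|---|---|---|
| 0.025 | 80% | 9 / (2.80 x 0.169) = 19.0 |
| 0.025 | 90% | 16.4 |
| 0.05 | 80% | 21.4 |
| 0.05 | 90% | 18.2 |

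I use 19, with 15 to 25 as a range. The SAP's power calculation uses the SD of post-treatment scores; applying the same value to change is a further assumption.

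**2. What can reach the test.** The test is group x time. With baseline and final visit it is the two-sample comparison of change. A constant surgeon difference in SNOT-22 level cancels within patient, so only a difference d in change remains in the error. For the same reason, with complete data, a surgeon main effect alone leaves the group x time test as it was. The term that acts is surgeon x time.

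**3. Share of variance due to surgeon.** R2 = q(1 - q)d^2 / SD^2, with q = 0.5 and SD = 19:
- d = 5: 0.25 x 25 / 361 = 0.017
- d = 10: 0.25 x 100 / 361 = 0.069

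**4. Effect on the standard error.** Unadjusted SE = 19 x sqrt(2/70) = 3.21. Adjusted SE = 3.21 x sqrt(1 - R2):
- d = 5: factor 0.991, a cut of 0.9%
- d = 10: factor 0.965, a cut of 3.5%
- d = 0: factor 1, no cut

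**5. Chance imbalance, if not stratified.** The SD of the between-arm difference in surgeon share is sqrt(2 x 0.25 / 70) = 0.0845. Multiplied by d, this adds error with SD 0.42 points (d = 5) or 0.85 points (d = 10). Compared with the SE, (0.42/3.21)^2 = 1.7% and (0.85/3.21)^2 = 6.9%. These are the R2 values of step 3, so it is the same quantity seen from another side.

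**6. Power** (margin 9, one-sided 0.025, 70 per arm, SD 19, q = 0.5). Adjustment moves power from 80.0% to 80.3% at d = 3, to 80.7% at d = 5 and to 82.2% at d = 9.

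**7. Sensitivity.** Over SD 15 to 25 and q 0.5 to 0.8, a surgeon difference of 3 to 9 points is 0.2% to 9% of variance, and adjustment adds about 0.1 to 2.2 percentage points of power.

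**8. LK score and infection.** The documents give no SD for LK and no infection rate, so no size can be computed for either.

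**The case against.** The strongest case against is that this is an optional covariate preference. Five parts of it deserve an answer.

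- *No surgeon effect on outcome is documented.* This stands. A reader might infer from the two habits that outcomes are known to vary by surgeon. The protocol shows only a difference in prescribing, and prescribing is what the randomized assignment replaces. Surgeon is plausible as a prognostic factor, no more.
- *Chance imbalance is not bias.* This stands. A reader might infer that an unadjusted analysis is distorted. Under unstratified randomization the imbalance is already reflected in the standard error and the test is valid. Under stratified randomization the unadjusted standard error is slightly too wide, which is conservative for non-inferiority. It would also be wrong to add lost precision and imbalance together as two harms (step 5).
- *The listed factors serve only exploratory and secondary analyses, and the wording may not be exhaustive.* True. But the primary model names no covariate at all, so surgeon is not covered there either.
- *Nothing says that the surgeon scores LK or declares infection.* This stands. Question 7 gives follow-up and data collection to physicians whose names are removed, and question 32 mentions an endoscopic check at one week. A rater effect on these outcomes is possible but not documented.
- *The SAP is written in the past tense.* If the analysis is complete, changing the primary model now would be post hoc. That limits the form of the fix; it does not remove the point.

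Pages were removed before review, so randomization details may exist elsewhere. The recommendation is the same with or without stratification.

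**Conclusion.** The point holds as a low-severity, nearly free improvement. Surgeon is not named in the primary SNOT-22 model, the LK model or the list of baseline factors, although patients come from two identifiable practices that differ on the treatment under test. The randomized comparison remains valid without it.

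The likely gain is a standard error about 0.9% to 3.5% smaller. This rests wholly on assumed values: SD 19, an equal split, 70 per arm and a 5 to 10 point surgeon difference in change. The documents supply none of these, and the gain is nil if the surgeons' patients change equally. The documents do not support reading this as a flaw that threatens the non-inferiority conclusion.

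**What to change.** - Add surgeon and surgeon x time to the SNOT-22 and LK repeated-measures models, or equivalently use surgeon as a two-level factor in a change-score model. A surgeon main effect alone is not enough.
- Report the infection risk difference stratified by surgeon (Mantel-Haenszel).
- Tabulate arm by surgeon, and state whether randomization was stratified by surgeon.
- If the analysis is already complete, keep the primary model as it is and report the adjusted results as a labelled sensitivity analysis.

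The cost is one degree of freedom in a change-score model, or two in the repeated-measures model with baseline and final visit. Surgeon should already be on record for every patient, so no new data are needed. If randomization was not stratified, fitting the factor is itself expected to inflate the variance by about 1/(140 - 1) = 0.7%, or some 0.4% in the standard error; the gains above do not deduct this.
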